5.2 Exclusion Criteria

Subjects meeting any of the following criteria must not be enrolled in the study.

- 1. Prior use of rituximab or any CD20 mAb for any reason.
- 2. Any contraindication to the use of rituximab.
- 3. Any prior therapy for FL (including but not limited to chemotherapy, radiotherapy).
- 4. Subjects who, in the opinion of the Investigator, require additional concomitant treatment for lymphoma.
- 5. Evidence of histologic transformation to high grade lymphoma or DLBCL.
- 6. Known Central Nervous System (CNS) involvement by lymphoma. (Note: CNS imaging not required unless clinically indicated).
- 7. Subjects on chronic supra-substitutive doses (defined as doses in excess of 7.5 mg per day of prednisone or prednisone equivalent for a period longer than 3 weeks) of systemic glucocorticoids.
- 8. Prior malignancy (including recurrence) within 5 years of screening, other than non-melanoma skin cancer or intraepithelial cervical neoplasia, which should have been successfully treated more than 1 year before study inclusion.
- 9. Subjects with any of the following: known seropositivity for or history of active viral infection with human immunodeficiency virus (HIV).
- 10. Subjects with positive serological test for hepatitis B surface antigen (HBsAg), hepatitis B core antibody (HBcAb) or hepatitis C virus (HCV) antibody can only be included in the study if any of the following is fulfilled.^{18,19}

- a. Subjects with a negative HBsAg and positive total HBcAb must have a HBV deoxyribonucleic acid (DNA) level <20 IU/mL (or 112 copies/mL) by polymerase chain reaction (PCR) to participate in the study. In addition, it is required for these subjects to follow consultation with a Hepatologist / relevant expert regarding initiation, monitoring, and use of HBV antiviral therapy and the subject must be willing to undergo PCR HBV DNA testing during treatment and agree to receive treatment as indicated. HBV DNA re-test will be performed as per the schedule of assessments (see Table 1–1) and further as needed, at the discretion of the Investigator.
- b. Subjects with a positive test because of HBV vaccination may be included (i.e., HBsAg negative, anti-HBs+, HBcAb–).
- c. Subjects positive for HCV antibody are eligible only if the PCR test for HCV ribonucleic acid (RNA) is negative.
- 11. Subjects with active tuberculosis (TB). Subjects with evidence of latent TB or a history of TB must have completed treatment or have initiated treatment for at least 1 month before the first dose of study drug (Day 1). If latent TB is suspected based on clinical or epidemiological grounds, it should be further investigated using the tuberculosis testing as appropriate following local practice or investigator judgment.
- 12. Subjects who have received a live vaccine within last 3 months or non-live vaccine within 4 weeks of the first administration of study drug. [Note: A need may arise for trial subjects to receive vaccine against COVID-19 while being a part of the study. All such decisions will be taken at the discretion of the Investigator in consultation with the CRO / Sponsor after due consideration to subjects' safety, national health policy of the respective country and overall need by the subject for such vaccine during the time of study participation].
- 13. Subjects with an active uncontrolled infection requiring systemic treatment at Screening or history of documented recurrent clinically significant infection within 6 months of study inclusion (e.g., 2 or more viral, bacterial or fungal infections requiring in-patient treatment).
- 14. Subjects with New York Heart Association (NYHA) class III or IV congestive heart failure or relevant arrhythmia or angina based on ECG with clinical judgment.
- 15. Subjects with known hypersensitivity to rituximab or its excipients, or to proteins of murine or other foreign origin.
- 16. History or presence of a medical condition or disease that in the Investigator's opinion would place the subject at an unacceptable risk for study participation.
- 17. Participation in any clinical study or having taken any investigational therapy during the 2-month period immediately preceding administration of the first dose of study drug.

- 18. Lactating or pregnant female.
- 19. Women of childbearing potential who do not consent to use highly effective methods of birth control (e.g., sterilisation, or other non-hormonal forms of contraception) during treatment and for at least 12 months after the last administration of study drug. True abstinence periodic abstinence (e.g., calendar ovulation, symptothermal, post ovulation methods) and withdrawal are not acceptable methods of contraception.
- 20. Subject has been previously randomised in this study.
- 21. Subject likely not to be available to complete all protocol required study visits or procedures.

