- ^{12.} Hepatitis B surface antigen, hepatitis B core antibody, HBV DNA (as applicable), HCV antibody, HCV RNA (as applicable), and human immunodeficiency virus to be conducted by local laboratory. HBV DNA at Screening, Week 12 and all visits from Week 12 onwards (only for subjects with history of hepatitis B or hepatitis B serology suggestive of past hepatitis B infection). Additional monitoring/management of subjects who were HCV antibody positive (and HCV RNA negative) at Screening should be done in accordance with local practice and standard of care.

[name] S.A.	
Protocol RI-01-006	

- ^{13.} Tumour assessments for the purpose of assessing subject eligibility (with central imaging confirmation) and medical care will be performed by the investigational site at Screening, Weeks 12, 28, and 52 (EOS/ET Visit) by reviewing CT scans (Neck, chest, abdomen, and pelvis) with contrast. Computed tomography scans obtained up to 6 weeks prior to the first administration of study drug may be used for determining study eligibility provided they are of adequate quality for subsequent central review. Tumour assessments may also be performed on the CT component of positron emission tomography computed tomography (PET-CT) scans with contrast if the quality of the CT part of PET-CT is equivalent to that of a standard CT. The same modality (CT or PET-CT) should be consistently used throughout the study evaluations. All imaging performed for the study will be forwarded to the central imaging vendor for review and assessment of response for the primary and other efficacy endpoints. Disease assessments are to be performed as scheduled according to Table 1–1, regardless of treatment delays resulting from toxicity. Care must be taken in scheduling disease assessments to prevent the introduction of bias based on treatment delays. Assessments are NOT to be scheduled based on the previous imaging time point, but rather Day 1 should be used as the Baseline when calculating when the on-study tumour assessments are to be performed (with consideration of visit windows).

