4.1 Overall Design

4.1.1 Description

This is a Phase III, randomised, multicentre, double-blind, parallel-group study in subjects with previously untreated, Stage II-IV, CD20-positive, LTB-FL.

It is planned to randomise approximately 312 subjects (Please refer Section 9.2) at approximately \geq 130 study sites worldwide.

The study will enrol subjects with CD20-positive, LTB-FL who are asymptomatic for lymphoma specific B-symptoms. LTB-FL will be assessed according to the GELF based criteria.^{3,9}

Subjects will receive induction treatment consisting of a weekly i.v infusion for 4 weeks (375 mg/m² of BSA) followed by maintenance treatment consisting of an i.v infusion (375 mg/m² of BSA) every 8 weeks from Week 12 up to Week 36.¹⁵

Randomisation will be stratified by low-, medium-, and high-risk subjects using the CCI CCI CCI CCI CCI CCI CCI (1-2 Vs. 3a) and geographical area (USA, Europe and Asia-Pacific region).

Subjects will attend study visits every week (± 2 days) during the Induction Treatment Period (Weeks 1 to 4), at Week 8 (± 7 days), at Week 12 (± 7 days), thereafter every 8 weeks (± 7 days) up to Week 52 (EOS/Early Termination [ET] Visit). Study procedures include physical examination, vital signs, Eastern Cooperative Oncology Group (ECOG) performance status, tumour assessments, clinical laboratory tests, serum LDH and β-2 microglobulin, coronavirus disease 2019 (COVID-19) testing at screening and as deemed appropriate by the Investigator at any time during the study, AEs, concomitant medication, immunogenicity, and PK and pharmacodynamic samplings for the subjects in the corresponding subset.

All subjects completing the study (Week 52) will attend an EOS Visit. Subjects discontinuing the study before Week 52 for any reason will also attend an ET Visit. Subjects positive for hepatitis B at screening will be followed up to 24 months post last dose of rituximab in the study as outlined in Section 6.10.

Subjects with a prior history of hepatitis B infection or serological tests suggestive of previous hepatitis B infection will continue to receive hepatitis B virus (HBV) antiviral prophylaxis therapy for at least 12 months post last dose of rituximab in the study and will be monitored and reported

for reactivation for up to 24 months following completion of rituximab therapy as outlined in Section 6.10.

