6.10 Guidance for Hepatitis B and Hepatitis C Seropositive Subjects

Subjects who show evidence of prior hepatitis B infection may participate in the study following consultation with a Hepatologist / relevant expert regarding monitoring and use of HBV antiviral therapy, and provided that subjects agree to receive and comply with HBV testing and hepatitis B prophylactic therapy as recommended by the Investigator, or treating Hepatologist, or relevant expert. HBV re-test will be performed as per schedule of assessment (see Table 1–1) and further at the discretion of the Investigator. ^{18,19}

Additional monitoring/management of subjects who had HCV antibody positive (and HCV RNA negative) at Screening should be done in accordance with local practice and standard of care.

Subjects will continue to receive HBV antiviral prophylaxis therapy for at least 12 months post last dose of rituximab in the study (i.e. 36 weeks, or earlier in case of ET), and will be monitored as recommended by hepatitis experts in accordance with local practice and guidelines. HBV reactivation will be monitored and reported for up to 24 months following completion of rituximab therapy. If any subject develops reactivation of HBV or any other significant infections while on rituximab, the Investigator should immediately discontinue study drug, consult with hepatitis experts, and institute appropriate treatment. For details and management of other infections, refer to the current marketed rituximab prescribing information. It will be the Investigator's responsibility to ensure compliance to the antiviral treatment, regular follow-up for monitoring (i.e. laboratory tests, clinical examination, AE evaluation) with the Hepatologist / relevant expert of hepatitis B seropositive subjects and reporting of any reactivation events to the Sponsor immediately during and post study follow-up period of 24 months post last dose of rituximab. The investigator has to periodically update to the Sponsor about all such follow-up visits, treatment compliance with antiviral and other medications, tests results, and hepatitis B reactivation for up to 24 months post last study dose of rituximab. Detailed procedure and the needed documentation to ensure compliance to post study follow-up and measures will be outlined in an amended study agreement between the Sponsor / Designee and the Investigator.

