10.6 Appendix 6: Protocol Amendment History

Amendment 1, 04 Jan 2019

Overall Rationale for the Amendment:

The protocol was amended based on protocol review non hold comments from the United States Food and Drug Administration (US FDA). One exclusion criterion was added to exclude patients with Central Nervous System involvement by lymphoma. Reference to statistical analysis plan was provided for detailed algorithm for sample size re-estimation and simulations to show that the type-I error rate will be maintained. The method to estimate difference (DRL_RI minus MabThera[®]) and its 95% Confidence Interval (CI) was updated to use exact Binomial method (Garner W, 2016; and Chan IS, Zhang Z, 1999); accordingly, the references were updated. In addition, a few edits were made for better clarity. The updates made to the protocol as presented in a tabular fashion below to reflect the changes made to the text in the previous version of the protocol (Version 1).

Amendment 2, 04 Dec 2019

Overall Rationale for the Amendment

The protocol was amended based on protocol review and recommendations by the Regulatory Authorities (United States Food and Drug Administration, US FDA). Other administrative changes/edits towards more clarity have also been made. These changes from the previous version of the protocol, are summarized in a tabulated manner below.

Amendment 3, 04 Nov 2020

Overall Rationale for the Amendment

This amendment allows for study inclusion of subjects with past history of hepatitis B or hepatitis B serology suggestive of past hepatitis B infection while ensuring that the management practices for this condition are in line with current scientific guidelines.

The protocol is also being amended to reflect contingency measures implemented by the Sponsor in the wake of the COVID-19 pandemic.

A few administrative and minor technical edits towards more clarity have also been made.

The changes from the previous version of the protocol are summarised in a tabulated manner below.

Amendment 1, 04 Jan 2019

S.	Section	Previous Protocol Text (Version 1)	Current Protocol Text (Version 2)	Brief Rationale
No	Number and			
	Name			
1	Sections 1.1 (synopsis) and 5.2; Exclusion Criteria	-	Criterion # 6: Known Central Nervous System (CNS) involvement by lymphoma. (Note: CNS imaging is not required unless clinically indicated.)	Addition of exclusion criterion based on protocol review non-hold comments from US FDA.

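### Exclusion criterion 10 shuts out HBsAg-positive subjects only by default and, read literally, leaves one narrow opening through its hepatitis C item

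*Protocol*

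**What the plan says.** Criterion 10 in Protocol Section 5.2 covers anyone with a positive test for HBsAg, HBcAb or HCV antibody. Such subjects "can only be included in the study if any of the following is fulfilled". The Synopsis uses the same lead-in. Three items follow:

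- Item a: "Subjects with a negative HBsAg and positive total HBcAb must have a HBV deoxyribonucleic acid (DNA) level" below 20 IU/mL. It also calls for consultation with a hepatologist or relevant expert and for willingness to undergo HBV DNA testing and treatment.
- Item b covers positivity due to HBV vaccination and specifies a negative HBsAg.
- Item c: "Subjects positive for HCV antibody are eligible only if the PCR test for HCV ribonucleic acid (RNA) is negative". It does not mention HBsAg or HBV DNA.

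Three other places deal with hepatitis B:

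- Section 6.10: "Subjects who show evidence of prior hepatitis B infection may participate in the study following" expert consultation. It later makes the investigator responsible for follow-up with the "relevant expert of hepatitis B seropositive subjects and reporting of any reactivation events to the Sponsor immediately".
- Section 4.1.1: "Subjects positive for hepatitis B at screening will be followed up to 24 months post last dose of rituximab in the study".
- Table 1–1, footnote 12, schedules HBV DNA testing at Screening and from Week 12 onwards, "only for subjects with history of hepatitis B or hepatitis B serology suggestive of past hepatitis B infection".

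**The concern.** The lead-in names HBsAg, but none of the three items is written for an HBsAg-positive subject. Exclusion therefore follows only from failing every item. That works unless a subject fulfils an item for an unrelated reason, and item c allows this. Past hepatitis C exposure with negative HCV RNA fulfils it, and the lead-in asks for only one item.

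The result is inverted. A subject with negative HBsAg and positive HBcAb must be below an HBV DNA limit and have expert consultation. A subject with positive HBsAg, which on ordinary clinical understanding is the higher-risk profile, could clear the same criterion with neither.

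The protocol treats reactivation as serious. Section 6.10 requires immediate discontinuation of study drug if it occurs, antiviral prophylaxis for at least 12 months after the last dose, and monitoring for up to 24 months. What is at stake is subject safety at entry, not the equivalence analysis.

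**Working it through.** The plan states no figure on this point, so the check is to apply the items to each relevant profile and then to look for any other text that closes the gap.

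**Step 1. Apply items a to c to each profile.**

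| Profile | Item a | Item b | Item c | Literal reading (one item is enough) | Marker-by-marker reading |
|---|---|---|---|---|---|
| HBsAg positive, HCV antibody negative | no (needs HBsAg negative) | no (needs HBsAg negative) | not met | excluded by default | excluded |
| HBsAg positive, HCV antibody positive, HCV RNA positive | no | no | no | excluded by default | excluded |
| HBsAg positive, HCV antibody positive, HCV RNA negative | no | no | **yes** | **not excluded** | excluded |
| HBsAg negative, HBcAb positive, HBV DNA below 20 IU/mL, HCV antibody negative | yes | no | not met | may enter under item a | may enter under item a |

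Only the third row departs from what the criterion appears to intend.

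**Step 2. See which hepatitis B conditions apply to the third row at entry.** The DNA limit and the consultation requirement in criterion 10 both sit inside item a, which is confined to HBsAg-negative subjects. Item c adds no hepatitis B condition.

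**Step 3. Look for an HBsAg rule elsewhere.**

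- Section 6.10 ties participation after consultation to prior infection. If it is read to cover an HBsAg-positive subject, it brings consultation, testing and prophylaxis, but no DNA limit and no rule on HBsAg.
- Footnote 12 of Table 1–1 provides for HBV DNA testing where serology suggests past infection. It gives no threshold for entry.
- Section 4.1.1 provides follow-up for subjects positive at screening. It is not an eligibility rule, but a site could take it to mean that such subjects may enrol.
- Criteria 2 (contraindication), 13 (active uncontrolled infection requiring systemic treatment) and 16 (unacceptable risk in the investigator's opinion) are general and do not name hepatitis B.

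**Step 4. Compare with the purpose.** Section 6.10 speaks of prior infection. The Amendment 3 rationale in Appendix 6, used here only as evidence of intent, reads "This amendment allows for study inclusion of subjects with past history of hepatitis B or hepatitis B serology suggestive of past hepatitis B infection". Neither suggests that HBsAg-positive subjects were meant to enter.

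**Step 5. Apply the proposed sentence.** With HBsAg-positive subjects excluded outright, the third row becomes excluded and the other rows keep the same result.

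**The case against.** The strongest reply is that the items are necessary conditions. Item a says what such subjects must have, and item c says when HCV-antibody-positive subjects are eligible. Neither says that a satisfactory hepatitis C result excuses a separate hepatitis B marker. Read marker by marker, each positive test needs its own permission; HBsAg has none, so every HBsAg-positive subject is out. This is probably what was meant, and it fits the references to prior and past infection. It stands as the better reading of intent. However, it asks the site to read the lead-in as requiring each marker to be cleared, when the text asks for only one item.

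The second reply is that enrolment is unlikely in practice. Criteria 2, 13 and 16 still apply, inclusion criterion 9 caps liver enzymes and bilirubin, HBsAg is a screening test, and eligibility is re-reviewed before randomisation. This also stands and keeps the point small. None of these is an HBsAg rule, and criterion 9 still allows AST and ALT up to 3 times the upper limit of normal.

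Two stronger readings are tempting, and the documents do not support them:

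- A reader might infer that criterion 10 has no rule at all for HBsAg-positive subjects. The lead-in admits seropositive subjects only if an item is met, which already excludes every HBsAg-positive subject who does not meet item c.
- A reader might infer that the whole combining phrase is faulty, so that HBsAg-negative, HBcAb-positive subjects above the DNA limit could enter through item c. Items a and c bind on their own terms, so this does not follow.

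**Conclusion.** The point holds in a narrow form. On a literal reading, criterion 10 does not exclude a subject who is HBsAg positive, HCV-antibody positive and HCV RNA negative, and no other current text sets an HBsAg rule or an HBV DNA limit for that subject at entry. All other HBsAg-positive subjects are already excluded by default.

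The conclusion rests on taking the lead-in at its word that one fulfilled item is enough; a marker-by-marker reading removes the gap. The size cannot be quantified because the documents give no frequency for this profile. A reader might infer that such subjects were enrolled, or that Section 4.1.1 deliberately admits them. The documents show neither, since Section 4.1.1 concerns follow-up. No efficacy analysis is affected. This is a minor wording repair to a safety entry rule.

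**What to change.** In Section 5.2 and in the Synopsis, add one sentence to criterion 10, placed outside the a to c list so that it cannot be treated as one more alternative: *Subjects positive for HBsAg are excluded.*

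This is enough by itself. The combining phrase can stay. Replacing it with a requirement to meet all items that apply is unnecessary and, if done without the new sentence, would make matters worse: no item applies to an HBsAg-positive, HCV-antibody-negative subject, who would then no longer be excluded by default.

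The cost is one sentence in two places. HBsAg is already part of viral screening in Section 8.1.1 and Table 1–1, so no test, visit or analysis changes.

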5.3 Screen Failures

Screen failures are defined as subjects who consent to participate in the clinical study but are not subsequently randomly assigned to study drug/entered in the study. A minimal set of screen failure information is required to ensure transparent reporting of screen failure subjects to meet the Consolidated Standards of Reporting Trials (CONSORT) publishing requirements and to respond to queries from regulatory authorities. Minimal information includes demography, screen failure details (reason[s] for the screening failure), eligibility criteria, and any serious adverse events (SAEs).

Individuals who do not meet the criteria for participation in this study (screen failure) may be rescreened at the Investigator's discretion, following discussion with the Sponsor designee MM. Subjects not included in the study due to latent TB (in the locations where TB screening is required) will also require rescreening after appropriate treatment has been administered as per local Guidance.

6 Study Intervention

6.1 Identity of Study Treatments

DRL_RI or MabThera[®] will be provided as study medication to the participating study sites.

6.2 Study Drugs Administered

This study is a randomised, double-blind, parallel-group, clinical study.

A computer-generated randomisation schedule will be used to assign subjects to the treatment groups. Subjects will be assigned a subject number in the order of their acceptance into the study. This identifying number will be retained throughout the study.

Following signing of informed consent, subjects will be registered into the study using an interactive web response system (IWRS) to receive a unique subject identification number. Randomisation will be performed using IWRS. Subjects will be randomised in a 1:1 ratio to one of the 2 study treatment arms taking into account stratification by low-, medium-, and high-risk subjects using the CCI index (CCI), tumour grade (1-2 Vs. 3a; i.e., subjects with Grade 1 tumours should be pooled with those with Grade 2 tumours, resulting in 2 levels for this factor), and geographical area (USA, Europe and Asia-Pacific region):

- Arm A: DRL_RI
- Arm B: MabThera[®]

The study drug DRL_RI or MabThera[®] will be administered as an intravenous (i.v) infusion, at a dose of 375 mg/m² of BSA.

Subject BSA will be calculated using an accepted formula. The Mosteller, Du Bois, and Haycock formulae are considered acceptable. The same formula should be used for the calculation of all doses administered to the same subject.

Mosteller formula²⁰:

 $BSA(m^2) = \sqrt{[Height\{cm\} x Weight \{kg\}]/3600)}$

Du Bois formula²¹:

 $BSA(m^2) = 0.007184 \text{ x Height (cm)}^{0.725} \text{ x Weight (kg)}^{0.425}$

Haycock formula²²:

 $BSA(m^2) = Weight (kg)^{0.5378} x Height (cm)^{0.3964} x 0.024265$

Subjects will receive induction treatment consisting of 4 weekly i.v infusions followed by maintenance treatment consisting of an i.v infusion every 8 weeks up to Week 36. Subjects will be pre-medicated before each infusion with an anti-pyretic and an antihistamine (e.g., paracetamol [acetaminophen] and diphenhydramine), and 100 mg i.v methylprednisolone or their equivalent to decrease the incidence and severity of acute IRRs.

First Infusion (Day 1): Initiate infusion at a rate of 50 mg/hour. In the absence of infusion toxicity, increase infusion rate by 50 mg/hour increments every 30 minutes, to a maximum of 400 mg/hour.

Subsequent Infusions: Initiate infusion at a rate of 100 mg/hour. In the absence of infusion toxicity, increase rate by 100 mg/hour increments at 30-minute intervals, to a maximum of 400 mg/hour.

Infusions should be administered under close medical supervision. The infusion should be interrupted, or the infusion rate slowed for infusion reactions. If symptoms improve the infusion rate can be continued at one-half the previous rate.

The schedule of dosing is presented in Section 1.2.

